7.3.2 Pfizer

The Principal Investigator will notify Pfizer of each Serious Adverse Event (SAE) encountered in the Clinical Trial within 24 hours of becoming aware of it, even if complete information is not yet available. This applies to SAEs which occur after the patient takes the first dose of study drug and continues until at least 30 days after the patient has stopped study treatment or is taken off-study, whichever comes first. Additionally, the Principal Investigator will notify Pfizer of any SAE the PI suspects has a causal relationship between the Pfizer Product and the SAE at any time after the patient's last study treatment. Information about all SAEs is collected and recorded on the Pfizer-provided Investigator-Initiated Research Serious Adverse Event Form; all applicable sections of the form must be completed in order to provide a clinically thorough report. The PI must assess and record the relationship of each SAE to each specific study treatment, complete the SAE Report Form and send the completed, signed form along with the Pfizer Reportable Event Fax Cover Sheet to the Pfizer US Drug Safety Unit [contact] within 24 hours of PI's awareness. To ensure patient safety, the Principal Investigator will also report each pregnancy, drug exposure during lactation, occupational exposure, and reportable instances of lack of effect as SAEs to Pfizer.

7.4 DATA AND SAFETY MONITORING PLAN

7.4.1 Principal Investigator/Research Team

The clinical research team will meet on a weekly basis when patients are being actively treated on the trial to discuss each patient. Decisions about dose level enrollment and dose escalation if applicable will be made based on the toxicity data from prior patients.

All data will be collected in a timely manner and reviewed by the principal investigator or a lead associate investigator. Adverse events will be reported as required above. Any safety concerns, new information that might affect either the ethical and or scientific conduct of the trial, or protocol deviations will be immediately reported to the IRB using iRIS.

The principal investigator will review adverse event and response data on each patient to ensure safety and data accuracy. The principal investigator will personally conduct or supervise the investigation and provide appropriate delegation of responsibilities to other members of the research staff.

8 STATISTICAL CONSIDERATIONS

The primary objective of this trial is to determine PFS of patients with low- or intermediate grade NET who receive first-line targeted therapy. This will provide preliminary data to explore whether the PFS on first-line therapy in patients treated with sunitinib or everolimus based on tumor genotyping may represent a potential improvement over published results with regular treatment with everolimus/sunitinib. Secondary objectives include evaluation of response and OS as well as safety and exploring the association between tumor genotype and PFS, and response to treatment.

If the findings suggest improved PFS from targeted treatment, a larger randomized trial to confirm the findings will be developed.

Following tumor genotyping, eligible patients will be treated with everolimus (Arm 2) or sunitinib (Arm 1). Based on results of the genotyping, enrolled patients will then receive targeted treatment with sunitinib (for mutations in *MEN1/PDGFR/KIT/FTL3* or everolimus (for mutations in *NF1/PTEN/PI3K/AKT/mTOR/VHL*). Patients with other different mutations or multiple types of mutations will be assigned to receive sunitinib since almost all of these tumors have elevated levels of VEGF/VEGFR expression.

Results from previously published trials[[53](#), [55](#)] both demonstrated approximately 11 months PFS in patients similar to the ones to be treated on this protocol. Those patients had not received cytoreductive surgery, and also were not assigned to receive treatment on the basis of any tumor genotype information. In the context of this trial, the study will be designed to determine if meaningful improvement in PFS may be obtained using this focused strategy. For purposes of sample size determination, patients will be primarily evaluated based on the treatment received. Thus, within each treatment arm, using the method of Brookmeyer and Crowley, with 44 patients accrued during a 48-month period (88 total patients for the two arms), and followed for up to an additional 12 months (60 months total from entry of the first patient), there would be 80% power to test whether the median PFS is consistent with 18 months, and greater than 11 months, with a 0.10 alpha level one-sided significance test.

In practice, a Kaplan-Meier curve of PFS will be constructed for each arm and will have the median as well as key time points such as 12 and 18 months estimated, along with appropriate

80% and 95% confidence intervals to explore whether the present results exceed those from prior studies. In addition, the Kaplan-Meier curves for all patients who received either sunitinib and everolimus as their treatments may be combined into one pooled Kaplan-Meier curve if the two curves for these treatments are sufficiently similar to one another ($p > 0.30$ by a two-tailed log-rank test). This combined curve will then be evaluated relative to the published median of 11 months PFS for each arm to provide a more powerful comparison relative to the historically expected results. In addition, Kaplan-Meier curves limited to the patients who received targeted therapy based solely on mutation status may be constructed for exploratory and descriptive purposes.

Response and overall survival will also be evaluated as secondary endpoints, based on the patients treated with sunitinib or everolimus, using all patients receiving treatment. These results will be descriptive and may consist of fractions of responses as well as Kaplan-Meier curves for survival. The association between genotype and PFS will be explored by evaluating the results within a treatment based on the major genotype categories identified. Safety will be evaluated by tabulating and reporting the distribution of the worst grade of each type of toxicity found, per patient, separately by arm. Should any particular type of toxicity result in 5 or more patients with grade 3-4 toxicity, a comparison of the distributions of toxicity between the two arms may be performed using a Cochran-Armitage test for trend.

Because the patients may not end up being assigned in equal proportions to the two arms, and because the goal is to have 44 evaluable patients who have received each treatment, additional patients beyond the 44 described above may be enrolled on the arm with faster accrual. As such, the study will have an accrual ceiling of 120 patients, with accrual ending when there are 44 evaluable patients on the arm with fewer patients. An amendment may also be needed if a lower proportion of patients than expected receive study drug therapy or if a high portion of treated patients are not evaluable for response. It is anticipated that 20-30 patients per year may enroll onto this trial; thus, accrual may be completed in 4-5 years.

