6.3.1 Definitions

Evaluable for toxicity: All patients will be evaluable for toxicity from the time of their first treatment with sunitinib or everolimus.

Evaluable for objective response: Only those patients who according to RECIST guideline (version 1.1) have measurable disease present at baseline, have been started on therapy with everolimus or sunitinib, and have had their disease re-evaluated will be considered evaluable for response. These patients will have their response classified according to the definitions stated below. (Note: Patients who exhibit objective disease progression prior to the end of cycle 1 will also be considered evaluable.)

Evaluable Non-Target Disease Response: Patients who have lesions present at baseline that are evaluable but do not meet the definitions of measurable disease, have been started on therapy with everolimus or sunitinib, and have had their disease re-evaluated will be considered evaluable for non-target disease. The response assessment is based on the presence, absence, or unequivocal progression of the lesions.

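### Sections 6.3.1 and 8 give conflicting denominators for response, and Section 8 counts accrual to 44 evaluable patients per arm without defining the term

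*Combined protocol and SAP*

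**What the plan says.** **Response set, 6.3.1.** Patients must have measurable disease at baseline, "have been started on therapy with everolimus or sunitinib, and have had their disease re-evaluated will be considered evaluable for response". Only these patients have a response classified. A note adds patients with objective progression before the end of cycle 1. A separate definition makes every treated patient evaluable for toxicity.

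**Response set, Section 8.** Response and overall survival are evaluated "using all patients receiving treatment".

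**Accrual, Section 8.** "the goal is to have 44 evaluable patients who have received each treatment". Accrual ends when the smaller arm has 44 evaluable patients, under a ceiling of 120. The term is not defined there. The following sentence foresees an amendment "if a high portion of treated patients are not evaluable for response".

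**Power, Section 8.** The calculation is made separately for each arm by the Brookmeyer-Crowley method. Its sample size is a count of accrued patients: "with 44 patients accrued during a 48-month period (88 total patients for the two arms"). Follow-up runs for a further 12 months once accrual closes. The claim is that "there would be 80% power to test whether the median PFS is consistent with 18 months, and greater than 11 months". The test is one-sided at alpha 0.10. Nothing in the calculation says that the 44 are evaluable patients.

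**PFS.** Section 6.3.6 counts progression or death from the start of each treatment. Section 8 plans a Kaplan-Meier curve for each arm, and possibly a pooled curve of all patients who received either drug. Neither is restricted to evaluable patients.

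**The concern.** An analyst who follows 6.3.1 computes the response rate in re-assessed patients, and one who follows Section 8 computes it in all treated patients. Neither section is said to take precedence. Under Section 8 a patient who was never re-assessed belongs in the denominator, yet 6.3.1 gives that patient no response. The best-response table for measurable disease in 6.3.4.3 has no row for target lesions that were never re-assessed.

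The choice matters because scheduled re-assessment first falls at 12 weeks (Section 6.3), and having no scan by then can itself be a result of the outcome, through early death or clinical deterioration. Excluding such patients moves the rate in one direction only. This is an uncontrolled trial read against published results, so no comparator arm would share the bias.

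The accrual rule adds a second ambiguity. If evaluable means evaluable for response, a treated patient with no re-assessment does not count towards 44 and enrolment continues past that patient. Section 8 does not say whether evaluability decides only when accrual stops, or also who is analysed.

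**Working it through.** **1. The plan's own power figure.** Inputs from Section 8: 44 per arm, null median 11 months, alternative 18, one-sided alpha 0.10 (z = 1.2816). With 12 months of follow-up after accrual there is no administrative censoring before 11 months, so the test can be approximated as a test of S(11) = 0.5. Assuming exponential PFS:

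- S(11) under the alternative = exp(-ln 2 × 11/18) = 0.6547.
- Null SE = √(0.25/44) = 0.0754. Alternative SE = √(0.6547 × 0.3453/44) = 0.0717.
- Power with the null SE for the critical value = Φ[(0.1547 - 1.2816 × 0.0754)/0.0717] = 79.1%.
- Power with the alternative SE throughout = Φ(0.1547/0.0717 - 1.2816) = 81.0%.

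The stated 80% reproduces for 44 patients per arm.

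**2. Who is affected.** Several provisions bring early stoppers to a scan or keep them in the 6.3.1 set:

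- The safety visit in 3.4 lists a radiological response evaluation, except after progression on both drugs. Section 3.5.1 holds that visit in all cases of removal from protocol therapy.
- Cross-over under 3.1.1 needs a CT or MRI within the preceding 4 weeks.
- The 6.3.1 note keeps objective progression in cycle 1.

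What remains is mainly death, deterioration or withdrawal with no post-baseline scan. The documents give no rate. As a guide to deaths alone, the median OS figures in 1.2.1 (2 years, 38 months, 5.8 years), taken as exponential, give 1 - exp(-ln 2 × 2.76/median) = 7.7%, 4.9% and 2.7% dead by week 12 (2.76 months).

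**3. Effect on the response rate.** All counts are assumed: 44 re-assessed patients, m treated patients never re-assessed, and responders as defined in 1.1.2 (CR + PR + SD).

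| m | 30 responders: 6.3.1 | 30 responders: Section 8 | 4 responders: 6.3.1 | 4 responders: Section 8 |
|---|---|---|---|---|
| 2 | 30/44 = 68.2% | 30/46 = 65.2% | 4/44 = 9.1% | 4/46 = 8.7% |
| 5 | 68.2% | 30/49 = 61.2% | 9.1% | 4/49 = 8.2% |
| 8 | 68.2% | 30/52 = 57.7% | 9.1% | 4/52 = 7.7% |

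The relative fall is m/(44 + m) whatever the number of responders. The absolute gap is larger here because the protocol's response rate includes stable disease.

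**4. PFS, as a conditional sensitivity only.** Suppose, contrary to any instruction in the documents, that early failures making up a fraction f of treated patients were dropped from the PFS test and accrual continued to 44. With a true median of 11 months, S(11) among those kept is s = 0.5/(1 - f). The apparent median is 11 × ln[1/(0.5(1 - f))]/ln 2. The chance of a positive test is Φ[(s - 0.5 - 1.2816 × 0.0754)/√(s(1 - s)/44)].

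| f (assumed) | Treated per arm for 44 | Apparent median (months) | Chance of a positive test |
|---|---|---|---|
| 0 | 44 | 11.0 | 0.10 |
| 2% | 45 | 11.3 | 0.13 |
| 5% | 47 | 11.8 | 0.18 |
| 8% | 48 | 12.3 | 0.24 |
| 10% | 49 | 12.7 | 0.29 |

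An exact binomial version (at least 27 of 44 event-free at 11 months) gives 0.09, 0.11, 0.16, 0.22 and 0.27. Under the exponential model with median 11, 1 - exp(-ln 2 × 3/11) = 17.2% have an event by 3 months. That is an upper bound on f, because progression documented on a scan leaves the patient evaluable.

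**The case against.** The strongest reply is that Section 8 is the analysis section and names all treated patients, whereas 6.3.1 only says whose response can be classified. Response is also a secondary endpoint reported descriptively, and most patients who stop early are scanned at the safety visit or before cross-over. Much of this stands. The affected group is small, and all treated patients is the more natural reading. It does not remove the conflict: 6.3.1 admits only re-assessed patients, and nothing says how an unscanned patient enters Section 8's denominator.

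A reader might go further and infer that early failures are left out of PFS and replaced, so that the primary test is biased. The documents do not support that:

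- Section 8 attaches no evaluability condition to PFS, and its pooled curve takes all patients who received either drug.
- Death is already a PFS event under 6.3.6.
- There is no replacement clause. Enrolment beyond 44 is explained by unequal allocation and the goal of 44 evaluable patients.
- Patients alive without a scan are not PFS events. The documents give no censoring rule, but under the usual one they add almost no follow-up whether kept or dropped. The sensitivity in step 4 therefore applies mainly to deaths before any scan, and its 10% row exceeds all three death estimates in step 2.

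What remains open on PFS is narrower. The all-patients wording is attached to the optional pooled curve, and the analysis set for the per-arm curves is never stated outright.

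**Conclusion.** The concern holds for response and for the accrual term. The two sections prescribe different response denominators, and the 6.3.1 rule excludes patients for reasons linked to outcome. For 2 to 8 unscanned patients beside 44 re-assessed, the assumed counts put the gap at 3.0 to 10.5 percentage points with 30 responders and 0.4 to 1.4 points with 4. The true number of unscanned patients is unknown. The accrual count rests on an undefined term that the adjacent wording ties to response, while the power is stated for 44 patients without that condition.

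The sample size is sound. Any PFS bias depends on the evaluable set being carried over to that analysis, which no section directs. The figures in step 4 rest on exponential PFS and assumed exclusion rates, and should be quoted only as a sensitivity.

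**What to change.** In 6.3.1, label the set evaluable for objective response as supplementary. In Section 8:

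- State that response, PFS and OS include every patient who took at least one dose of study drug.
- State that patients with no post-baseline scan count as non-responders.
- Define *evaluable*, and either say that it governs accrual only and never the analysis set, or count the 44 per arm as treated patients.

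This changes wording only. The reported response rate may be slightly lower than under 6.3.1. The stated power is unchanged: 44 treated patients per arm still give about 79% to 81%. If evaluability is kept for accrual, the extra treated patients (for example 47 per arm at an assumed 5% unscanned) stay in the analysis.

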9 COLLABORATIVE AGREEMENTS

9.1 COOPERATIVE RESEARCH AND DEVELOPMENT AGREEMENT (CRADA)

The everolimus used in this trial in NCI will be obtained under a CRADA (02975) with Novartis, the manufacturer of the agent.

9.2 CLINICAL TRIALS AGREEMENT (CTA)

The sunitinib used in this trial in NCI will be obtained under CTA with Pfizer (00963-14), the manufacturer of the agent.

10 HUMAN SUBJECTS PROTECTIONS

10.1 RATIONALE FOR SUBJECT SELECTION

Subjects from both gender groups and all racial/ethnic groups are eligible for this study if they meet the eligibility criteria. Efforts will be made to extend accrual to a representative population.

10.2 PARTICIPATION OF CHILDREN

Patients age 18 and older will be eligible for this study. The incidence and prevalence of metastatic pancreatic and gastrointestinal neuroendocrine tumors in the pediatric patient population is exceedingly rare and this is the rationale for not including this patient population.

10.3 PARTICIPATION OF SUBJECTS UNABLE TO GIVE CONSENT

Adults unable to give consent are excluded from enrolling in the protocol. However re-consent may be necessary and there is a possibility, though unlikely, that subjects could become decisionally impaired. For this reason and because there is a prospect of direct benefit from research participation (Section 10.5), all subjects will be offered the opportunity to fill in their wishes for research and care, and assign a substitute decision maker on the “NIH Advance Directive for Health Care and Medical Research Participation” form so that another person can make decisions about their medical care in the event that they become incapacitated or cognitively impaired during the course of the study. Note: The PI or AI will contact the NIH Ability to Consent Assessment Team (ACAT) for evaluation as needed for the following: an independent assessment of whether an individual has the capacity to provide consent; assistance in identifying and assessing an appropriate surrogate when indicated; and/or an assessment of the capacity to appoint a surrogate. For those subjects that become incapacitated and do not have pre-determined substitute decision maker, the procedures described in NIHMEC Policy 87-4 and NIH HRPP SOP 14E for appointing a surrogate decision maker for adult subjects who are (a) decisionally impaired, and (b) who do not have a legal guardian or durable power of attorney, will be followed.

10.4 EVALUATION OF BENEFITS AND RISKS/DISCOMFORTS

10.4.1 Risks/Benefits Analysis

The risks and benefits of participation for adults who become unable to consent, are no different than those described for patients who are less vulnerable.

10.4.1.1 Risks

10.4.1.1.1 Study Drug Risks

The risks of participation in this study are primarily associated with the toxicities of the study agents as discussed in Section 11. Both study agents have been approved by the FDA for the treatment of progressive, locally advanced or metastatic pancreatic NETs and have been available for clinical use since 2011. Patients will be monitored routinely in order to minimize the risk of complications.

10.4.1.1.2 Specimen Collection Risks

Risks also include those associated with specimen collection include pain, bleeding and the possibility of infection at the sampling site. Risk of baseline biopsy: All care will be taken to minimize risks that may be incurred by tumor sampling. However, there are procedure-related risks (such as bleeding, infection and visceral injury) that will be explained fully during informed consent. If patients suffer any physical injury as a result of the biopsy, immediate medical treatment is available at the enrolling center. Although no compensation is available, any injury will be fully evaluated and treated in keeping with the benefits or care to which patients are entitled under applicable regulations.

10.4.1.1.3 Risk of Radiation

This research study involves exposure to radiation from one CT guided biopsy. This radiation exposure is not required for medical care and is for research purposes only. The amount of radiation received in this study is 0.80 rem which is below the guideline of 5 rem per year allowed for research subjects by the NIH Radiation Safety Committee. The average person in the

United States receives a radiation exposure of 0.3 rem per year from natural sources, such as the sun, outer space, and the earth's air and soil. More information about radiation is available in the pamphlet, An Introduction to Radiation for NIH Research Subjects.

10.4.1.1.4 Non-Physical Risks of Genetic Research

- Risk of receiving unwanted information

Anxiety and stress may arise as a result of the anticipation that unwanted information regarding disease related DNA sequencing or disease tendencies, or misattributed paternity. Patients will be clearly informed that the data related to DNA sequencing and genetic analysis is coded, investigational and will not be shared with patients, family members or health care providers.

- Risk related to possibility that information may be released

This includes the risk that data related to genotype, DNA sequencing or risk for disease tendency or trait can be released to members of the public, insurers, employers, or law enforcement agencies. Although there are no plans to release results to the patients, family members or health care providers, this risk will be included in the informed consent document.

- Risk to family or relatives

Family members or relatives may or may not want to be aware of familial tendencies or genetic risks of disease which may cause anxiety about possible future health problems. As previously noted, patients will be given the option in the consent document to be notified of any medically significant and actionable incidental findings.

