5.3.4 Management of Results

The results of molecular studies will be communicated to the patient. Other than initial determination of the presence of particular genetic alteration(s) outlined in **Appendix C** and **Appendix D**, the results of subsequent molecular studies are for research purposes only and will not be communicated to the patient. The exceptions to this are potential incidental findings that are deemed medically significant and actionable.

Subjects, treated in NCI will be contacted if a clinically actionable gene variant is discovered. Clinically actionable findings for the purpose of this study are defined as disorders appearing in the American College of Medical Genetics and Genomics recommendations for the return of incidental findings that is current at the time of primary analysis. (A list of current guidelines is maintained on the CCR intranet: <https://ccrod.cancer.gov/confluence/display/CCRCRO/Incidental+Findings+Lists>). Subjects who still remain on the study will be contacted at this time with a request to provide a blood sample to be sent to a CLIA certified laboratory.

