5.3.4.1 Genetic counseling in NCI

If the research findings are verified in the CLIA certified lab, the subject will be offered the opportunity to come to NIH (at our expense) to have genetic education and counseling with the NCI Genetics Branch to explain this result. If the subject does not want to come to NIH, a referral to a local genetic healthcare provider will be provided (at their expense). This is the only time during the course of the study that incidental findings will be returned. No interrogations regarding clinically actionable findings will be made after the primary analysis

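### The risk text in 10.4.1.1.4 says sequencing results will not reach patients or clinicians, but 5.3.4 returns them and the design assigns treatment by them; the sections need reconciling and the consent checking.

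*Combined protocol and SAP*

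**What the plan says.** Section 10.4.1.1.4 (Non-Physical Risks of Genetic Research) has three bullets.

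- The first sets out what patients are to be told: that sequencing and genetic analysis data "is coded, investigational and will not be shared with patients, family members or health care providers".
- The second, on accidental disclosure, opens: "Although there are no plans to release results to the patients, family members or health care providers".
- The third, on relatives, says that "patients will be given the option in the consent document to be notified of any medically significant and actionable incidental findings".

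Section 5.3.4 (Management of Results) begins: "The results of molecular studies will be communicated to the patient". It then sets aside the initial determination of the Appendix C and D alterations and says of everything after it that "the results of subsequent molecular studies are for research purposes only and will not be communicated to the patient". It qualifies that limit too: "The exceptions to this are potential incidental findings that are deemed medically significant and actionable". It goes on: "Subjects, treated in NCI will be contacted if a clinically actionable gene variant is discovered". Section 5.3.4.1 offers counseling at NIH on verified findings, or referral to a local genetics provider.

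The first-line arm depends on the result. Section 2.3.1 defines the two cohorts by mutation. Section 3.1 assigns the drug by tumor genotype or germline status. The footnote to Table 3 (Section 3.2.2) covers wild-type tumors and unlisted genes, and Section 8 confirms assignment from genotyping.

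**The concern.** The first bullet of 10.4.1.1.4 is more than background: it directs what patients are told about their genetic data. Taken at its word, it tells them that neither they nor their clinicians will see the results. In a trial named for mutation-targeted therapy that cannot be so, because the treating team must have the result to select the arm.

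What is at stake is the accuracy of consent on a point patients and relatives may care about. Section 5.3.1 sequences 197 genes in tumor and in germline DNA, and the Appendix C list includes hereditary cancer genes such as BRCA1, BRCA2, MLH1 and MSH2. Whether such a result may come back to the patient is material to the decision to take part.

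**Working it through.** No formula applies, and the plan gives no figure to reproduce. The check sorts genetic results into three kinds and compares what each section does with them.

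| Kind of result | 10.4.1.1.4, bullets 1 and 2 | 10.4.1.1.4, bullet 3 | 5.3.4 and 5.3.4.1 | Arm assignment (2.3.1, 3.1, Table 3, 8) |
|---|---|---|---|---|
| Genotype or germline result used for assignment | Not shared with patient or clinicians | Silent | Told to the patient | Needed by the treating team |
| Later, research-only results | Not shared | Silent | Not told to the patient | Not needed |
| Actionable incidental findings | Not shared | Patient may choose to be told | Returned; counseling or outside referral | Not needed |

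1. Row 1 is a direct conflict. Section 5.3.4 returns this result to the patient, and assignment cannot proceed unless clinicians have it. Every genotype outcome leads to a drug: listed mutations go to one arm or the other, while wild-type and unlisted mutations go to sunitinib.
2. Row 2 agrees. This is the only kind of result for which the first two bullets fit Section 5.3.4.
3. Row 3 conflicts with the first two bullets twice: with 5.3.4 and 5.3.4.1, and with the third bullet of the same section. The referral in 5.3.4.1 brings in an outside clinician as well.
4. Could the first two bullets be read as covering row 2 only? That requires a limit to subsequent research studies, which they do not contain. Section 5.3.4 states that limit in so many words when it intends it.
5. Who is covered? The risk statement applies to all participants, up to the accrual ceiling of 120 (Section 8). Germline DNA is planned for every patient (Table 3 footnote). Tumor biopsy for genotyping is not required in known MEN1, VHL or NF1 (Sections 2.1.1.4 and 2.4). For those patients an already known germline diagnosis can set the arm.
6. Who would be contacted about an actionable variant? Section 5.3.4 limits this to subjects treated at NCI and makes the request for a confirmatory sample to those still on study. Section 5.3.4.1 rules out further searching for such findings after the primary analysis. The number contacted would be some fraction of 120 that the documents do not let one compute.

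**The case against.** The best defense is context. Section 10.4.1.1.4 concerns genetic research and describes coded, investigational data, so its author probably had the later research studies in mind. The operating rule sits in Section 5.3.4, and the rest of the protocol is so plain about genotype-based assignment that no one would keep the result from the treating team. This stands as an account of how the wording arose, and it makes any effect on assignment implausible. It does not repair the text, because the reading works only by adding a qualifier that is absent.

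Four stronger readings are tempting and are not supported.

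- A reader might infer that every patient consents on a false statement. The consent form is not in the documents, and the third bullet says it offers notification of actionable findings. What patients are actually told cannot be judged here.
- A reader might infer that staff following 10.4.1.1.4 would withhold actionable germline findings. Its third bullet provides for notifying patients who choose it, so at most those who did not choose it would go uninformed.
- A reader might infer that the consent option and the contact rule in 5.3.4 contradict each other. Section 5.3.4 does not mention the option, but contacting only those who took it would satisfy both. This is an ambiguity to settle.
- A reader might infer that all 120 patients have trial tumor sequencing and may be contacted. The familial-syndrome exception and the limits on contact rule that out.

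**Conclusion.** The concern holds as an internal conflict in the protocol. The first two bullets of 10.4.1.1.4 are wrong for two of the three kinds of genetic result: the one used for assignment and actionable incidental findings. They conflict with Sections 5.3.4 and 5.3.4.1, with the assignment rule, and with their own section's third bullet.

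The statement reaches every participant, up to 120. Whether anyone is misinformed depends on one thing the documents do not show: whether the consent form repeats the first two bullets. The correction is worth making because it bears on patient protection and costs little. Nothing in the sample size, power, endpoints or analysis depends on it.

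**What to change.** Revise 10.4.1.1.4 to follow the three kinds of result.

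1. State that the genotype or germline result used for assignment is known to the treating team and communicated to the patient.
2. Limit the first two bullets to subsequent research-only results.
3. Name actionable incidental findings as the exception, as 5.3.4 already does.
4. Settle one notification rule and put it in both 10.4.1.1.4 and 5.3.4: either contact depends on the choice made in the consent, or it does not. Keep the limit to NCI-treated subjects still on study visible in both places.
5. Compare the consent form with the revised text and correct it where it follows the present first two bullets.

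The cost is protocol wording at the next amendment, plus consent wording if the check in step 5 shows it is needed. No design or analysis element changes.
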